factors leading to this complex disease are thought to be the cause that can result in lesions

(small areas of damage) in the brain and spinal cord, the central nervous system (CNS). These

lesions are thought to be the cause of relapses and disability in MS.

Condition: Multiple Sclerosis, Relapsing-Remitting

Intervention

Drug: A (oral cocktail formula of structured lipids),

Drug: B (PLP10) (oral cocktail formula of structured molecules, lipids and vitamins),

Drug: C (antioxidant vitamin),

Drug: Placebo (virgin olive oil)

Phase: II (Proof-of-Concept)

Investigator/Trial Location: By PALUPA Medical Ltd. At The Cyprus Institute of Neurology and

Genetics

Study Type: Interventional

Study Design: Allocation: Randomized

Endpoint Classification: Efficacy /Safety Study

Intervention Model: Parallel Assignment

Masking: Double Blind (Subject, Investigator, Total involved Personnel,

Outcomes Assessor)

Primary Purpose: Treatment/adjuvant treatment

Investigator Specialties: Neurology, Clinical Biochemistry (Lipidology, Immunology) and Clinical

Dietitian. All investigators are experienced and with more than 20 years in practice.

Enrollment: Total number of MS patients in Cyprus meeting the required criteria.

Arms	Assigned Interventions
Group 1: Experimental	Drug: A†
A, Oral Intervention: Drug: A (structured lipids)	Cocktail of EPA/DHA re-esterified triglycerides, triglycerides of LA/GLA, vitamins A, E as alpha tocopherol, 15.3 ml, oral, daily 30 minutes before dinner, for 30 months.
Group 2: Experimental	Drug: PLP10†
B-PLP10, Oral Intervention: Drug: B-PLP10 (structured lipids and vitamins)	Cocktail of EPA/DHA re-esterified triglycerides, triglycerides of LA/GLA, vitamins A, E as alpha tocopherol, E as gamma tocopherol, 16.0 ml, oral, daily 30 minutes before dinner, for 30 months.
Group 3: Experimental	Drug: C†
C, Oral Intervention: Drug: C (antioxidant vitamin)	Gamma tocopherol (vitamin E isoform/antioxidant), 760 mg (in pure virgin olive oil as a vehicle), 17.0 ml oral, daily 30 minutes before dinner, for 30 months.
Group 4: Placebo Comparator	Drug: Placebo†
D-Placebo Oral Intervention: Drug: Placebo	Placebo (Pure Virgin Olive Oil), 17.0 ml, oral, daily 30 minutes before dinner, for 30 months.

Preparations for the daily intervention formula agent dosages will be:

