Intervention formula A daily dosage: EPA (1650mg) / DHA (4650mg) / GLA (2000mg) / LA (3850mg) / total other omega-3 (600mg) / total monounsaturated fatty acids (MUFA) (18:1 1300mg, 20:1 250mg, 22:1 82mg, 24:1 82mg) + total saturated fatty acids (SFA) (18:0 160mg,

16:0 650mg) / vitamin A (0.6mg) / vitamin E (22mg).

Intervention formula B (PLP10) daily dosage: EPA (1650mg) / DHA (4650mg) / GLA (2000mg) / LA (3850mg) / total other omega-3 (600mg) / total MUFA (18:1 1300mg, 20:1 250mg, 22:1 82mg, 24:1 82mg) + total SFA (18:0 160mg, 16:0 650mg) / vitamin A (0.6mg) / vitamin E (22mg) / gamma- tocopherol (γ-tocopherol) (760 mg).

Intervention formula C daily dosage: γ -tocopherol (760 mg) (in 16137 mg pure virgin olive oil as a vehicle).

Intervention formula D daily dosage: pure virgin olive oil (16930mg).

† Citrus aroma will be added in each intervention formula to make up a total dosage of 19.5ml of solution per day.

Stabilization and Standardization by supplier

Intervention Preparation

The specific omega-3 (re-esterified glycerides) and omega-6 (glycerides) raw materials will be purchased according to the required interventions' fraction structural, quantity/ratio and quality specification (vitamin E (alpha-tocopherol) will be used as antioxidant stabilizer by the supplier). The Vitamins and food grade masking aroma will be purchased separately. The mixing of fractions to the final required intervention composition specification will always be performed by the same team of scientists under the supervision of the involved medical biochemist and lipidology specialist, under appropriate conditions every six months. Interventions will be stored refrigerated in dark until use.

Inclusion Criteria

- Men and women
- Ages of between 18 and 65 years
- Diagnosis of relapsing remitting Multiple Sclerosis (RRMS) according to McDonald criteria
- A score of 0.0 to 5.0 on the Expanded Disability Status Scale (EDSS)
- At least one medically documented relapse within the 18 months before enrollment

- Cranial MRI scan demonstrating lesion(s) consistent with MS
- On Interferon beta (IFN-β), glatiramer acetate treatment for the last 6 continuous months or more, or on no treatment

Exclusion Criteria

- Prior immunosuppressants or monoclonal antibodies (natalizumab should be available in the market in 2006) therapy
- A recent (<30 days) relapse
- Pregnancy or nursing
- A clinically significant infectious illness within 30 days prior to randomization

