- Primary progressive, secondary progressive or progressive relapsing MS
- Patients known to have a history of recent drug or alcohol abuse
- Any severe disease other than MS compromising organ function, meaning: history of, or abnormal laboratory results indicative of any significant cardiac, endocrinologic, hematologic, hepatic, immunologic, metabolic, urologic, pulmonary, gastrointestinal, dermatologic, renal and/or other major disease, that in the opinion of the investigators, would preclude the administration of PLP10 for 30 months.
- History of severe allergic or anaphylactic reactions or known specific nutritional hypersensitivity.

Note

During "on intervention treatment" the patients (depending on their pathological status) will be treated according to the normal international guidelines. A thorough record of treatment (or change of treatments) for each patient will be kept. If a patient changes therapy to immunosuppressant or monoclonal antibody or any other treatment on physicians' decision then he/she will be considered as a drop-out; but continue to be medically followed for the intention to treat analyses purposes.

If a clinical documented relapse is reported during "normalization" period the entry baseline EDSS for that patient will be reported as the EDSS score documented at least 4 weeks after the last relapse during this period.

"Normalization period" will be a 6 months period between enrolment and entry baseline (the first 6 months of the trial that patients will be on the intervention treatment for only normalization purposes). For the result analyses this 6 month period will be considered as a period before entry baseline for all four treatment arms.

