CING is a tertiary accredited neurological center. All patients should give a written informed consent before enrolment. The study protocol is developed by the investigators and should be approved by the National ethics committee. Patient consent forms (CFs) and case report forms (CRF) documents are set up by the investigators according to the international guidelines and the needs of the trial protocol/ design and approved by the independent committee assigned by the funder. Study data (CRFs will be completed as required per patient per assessment) will be collected by the involved neurologist and forwarded to be held and blindly analyzed centrally according to the guidelines set-up by the Helix Incubator Organization of Nicosia University (HIONU) as an independent organization assigned by the funder. A CRF copy should be kept by

the clinical site. During the study, investigators and safety/ monitoring committee representatives should meet once a year to discuss study progress.

Randomization and Masking

Patients will be randomly assigned to the four intervention groups. Randomization will be centralized and the randomization scheme will be generated, performed and securely stored by HIONU.

Sample size as a result of the absence of any previous reported data and due to the novelty of the intervention will strictly be based on the total eligible to participate relapsing remitting MS patients in Cyprus.

Responsibilities will include, but not limited to regulatory management, clinical trial management, quality control (use only of accredited laboratories) and administrative activities. External committees (ie. independent safety/ monitoring committee etc.) will be set up by the funder. Randomization scheme will be securely stored by HIONU, with the investigators, patients, all study personnel, medical monitors, clinical research associates, statisticians/bioanalysts, neuroradiologist and pharmacist being unaware of treatment assignments throughout the study.

If knowledge of the study drug will be needed to manage a patient's condition, such as in the occurrence of a serious adverse event, the patient will not be given further treatment with the study drug and should continue to be medically followed.

Study Procedures and End Points

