The key secondary endpoint is the **time to confirmed disability progression** defined as an increase of 1.0 on the EDSS from a baseline score, confirmed after 6 months, with an absence of an ongoing relapse at the time of assessment (progression cannot be confirmed during a relapse) and with no documented relapse during the 6-months period needed for the confirmation. The final EDSS score will also be confirmed 6 months after the end of the study.

Relapses should be treated with methylprednisolone at a dose of 1g intravenously per day, for three consecutive days followed by prednisolone by mouth at a dose of 1mg/kg of weight per day on a tapering scheme for three weeks.

Hematological (full blood count) and Biochemical analyses should be performed at enrolment, baseline, 12 months and 24months and at the end of the extended period; performed at accredited laboratory.

Blood should be collected from all randomized patients at the time of enrolment and at every scheduled clinical assessment and during relapses. Blood tubes should be appropriately labelled including date, patients' code, number of scheduled assessment, for every blood handling step. A portion of 2 ml total blood volume per patient (in anticoagulant solution) should be drawn and stored refrigerated (4°C) for the lipid extraction procedure (from red blood cells) within 24 hrs according to standard protocol.

Sample Size Estimation

Power calculations could not be done before the study because of the lack of information from previous studies on potential effect sizes. Based on the population size of our country and the centre of reference (CING) we believe that we will probably be able to enroll enough patients for this proof-of-concept study. The scientific knowledge/background of the agents used, novelty of the assessed interventions and the study-protocol design/set-up will be contributing to valuable information. Hopefully the "eligible" final enrolled sample size will be enough to collect quality data able to answer the addressed proof-of-concept questioned - efficacy indication. There is no any matter of ethical conflicts since all interventions will be used as adjuvant. Sample size will strictly be based on this subjects' availability parameter.

Brief Statistical Methods

The study will be considered successful if there is a significant difference between the treatments for either of the two endpoints.

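### The protocol calls every intervention adjuvant but admits untreated patients: the statement needs correcting, and randomisation should be stratified by background treatment

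*Protocol*

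**What the plan says.** Four parts of the protocol bear on this.

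- **Sample Size Estimation.** No power calculation was possible, and the sample size rests on the number of available patients. The section then adds: "There is no any matter of ethical conflicts since all interventions will be used as adjuvant".
- **Inclusion Criteria.** Eligible background treatment is: "On Interferon beta (IFN-β), glatiramer acetate treatment for the last 6 continuous months or more, or on no treatment".
- **Design summary.** "Primary Purpose: Treatment/adjuvant treatment".
- **Note after the Exclusion Criteria.** During the trial patients "will be treated according to the normal international guidelines". A patient who changes to an immunosuppressant, a monoclonal antibody "or any other treatment on physicians' decision then he/she will be considered as a drop-out", but is still followed for the intention-to-treat analysis. Background therapy is documented: "A thorough record of treatment (or change of treatments) for each patient will be kept".

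On allocation, Randomization and Masking says "Patients will be randomly assigned to the four intervention groups", under a central scheme generated and held by HIONU. It names no stratification factor. Brief Statistical Methods allows pre-specified covariates in the relapse-rate and Cox models without naming any.

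**The concern.** A product is adjuvant only if it is added to something. A patient who enters on no disease-modifying treatment, and stays so, receives the study oil (in group 4, olive oil) with no such treatment alongside it. The claim that all use is adjuvant therefore describes a narrower trial than the eligibility criteria create, and it is the only reason that section gives for the absence of an ethical conflict.

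The statistical consequence is more modest. Each formula-versus-placebo contrast is an average over two kinds of use, in proportions the protocol does not fix. A reader who takes the adjuvant sentence at face value would describe the result as an effect on top of interferon beta or glatiramer, which the design does not estimate. If background treatment also predicts relapse and the arms are small, a chance difference in the untreated share can move the observed relapse-rate ratio in the one allocation that is actually drawn.

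**Working it through.** **Step 1: the texts side by side.** The protocol states no sample size, relapse rate or power, so there is no figure to reproduce.

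| Place | Use that it implies |
|---|---|
| Sample Size Estimation | adjuvant for all |
| Inclusion Criteria | adjuvant for some, sole therapy for others |
| Design summary | treatment and adjuvant treatment |

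The first row is incompatible with the second and does not fit the third. Guideline-based care during the trial does not repair it: the guidelines may leave a patient untreated, and the Note classes a patient who changes to another treatment as a drop-out.

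**Step 2: how often the arms would differ.** These inputs are assumptions, not figures from the protocol: *n* patients per arm, a proportion *p* on background treatment, unstratified allocation. For one active arm and placebo, each with a Binomial(*n*, *p*) count on treatment, the exact probability that the shares differ by 20 points or more is the sum of P(i)·P(j) over all pairs with |i − j|/*n* ≥ 0.20:

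| *n* per arm | 50% untreated | 30% untreated | 10% untreated |
|---|---|---|---|
| 20 | 26.8% | 22.6% | 6.3% |
| 30 | 15.5% | 12.0% | 1.8% |
| 50 | 5.7% | 3.8% | 0.2% |

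**Step 3: what such a gap does.** Let *r* be the relapse rate on background treatment relative to none (assumed 0.5 to 0.8), and let a and b be the treated shares in the active and placebo arms. With no true effect of the formula, the expected ratio is (a·r + 1 − a)/(b·r + 1 − b). For 60% versus 40%:

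- *r* = 0.5: 0.70/0.80 = 0.875, a shift of 12.5%
- *r* = 0.67: 0.802/0.868 = 0.924, a shift of 7.6%
- *r* = 0.8: 0.88/0.92 = 0.957, a shift of 4.3%

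For 80% versus 60% the shifts are slightly larger: 14.3%, 8.2% and 4.5%.

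**Step 4: size against sampling error.** Further assumptions: untreated rate 1.0 per year, 2 years of follow-up, half on treatment, *r* = 0.67, gamma overdispersion 0.5, 20 per arm. Expected counts are 2 (untreated) and 1.34 (treated).

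- Mean count: (2 + 1.34)/2 = 1.67
- Variance: 1.67 + 0.5 × (4 + 1.796)/2 + 0.33² = 1.67 + 1.449 + 0.109 = 3.228
- Standard error of the log rate ratio: √(2 × 3.228/20)/1.67 = 0.34
- Shift from Step 3: ln 0.924 = −0.079, about a quarter of one standard error
- Share of count variance due to background: 0.109/3.228 = 3.4%. The same formula gives 8.3% at *r* = 0.5 and 1.1% at *r* = 0.8.

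**Step 5: effect on the test.** A simulation of an unadjusted comparison used the Step 4 assumptions with *r* = 0.5 or 0.67, 20 to 50 per arm and 40,000 runs per setting. The mean rate ratio over all allocations was 1.00 and the two-sided type I error was 5.4-6.4% against a nominal 5%; the slight excess is put down to the small-sample Wald test. Among allocations with a gap of 20 points or more it was 6.7-10.8%.

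**The case against.** The strongest reply is that this is loose wording and no more. Three parts of that reply stand.

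- **Sizing.** A reader might infer that the sample size rests on an add-on background. It does not: the section assumes no rate, effect or background, so no sizing input is wrong.
- **Confounding.** A reader might infer that the placebo contrasts are confounded. Under randomisation an imbalance is chance error, which the test covers on average; the distortion in Step 5 appears only after conditioning on an unlucky allocation. The same is true of any prognostic factor.
- **Covariates.** A reader might infer that the analysis ignores background treatment. The protocol provides for pre-specified covariates, and naming them may properly be left to the analysis plan, which is not at hand.

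It is also fair that a mixed-background population is a legitimate choice. Missing Data Handling asks whether the interventions reduce relapses in relapsing-remitting patients, and a randomised average over that population answers the question. The protocol's silence on stratification does not prove that allocation will be simple, and the figures in Step 2 depend on that.

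A further inference concerns the per-protocol analysis, which the protocol makes the key one. If untreated patients who start therapy leave that set, and do so more often on placebo, the background mix could diverge for reasons that randomisation does not control. The mechanism is possible, but the protocol gives nothing from which to judge its frequency, so no weight is placed on it here.

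The reply does not dispose of the word *all*. The eligibility criteria contradict it, and an analysis plan cannot correct an untrue statement in the protocol. Stratification also has to be settled before enrolment.

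**Conclusion.** The point holds in a limited form. The statement that all interventions are adjuvant is untrue for patients who enter and remain untreated, so the ethical ground resting on it does not match the eligibility criteria, and each placebo contrast estimates a pooled add-on and sole-therapy effect. The sizing is unaffected, and the comparison of patients as randomised is unbiased on average.

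The remaining statistical risk is conditional and depends on arm size. With 20 per arm and 30-50% untreated, about one unstratified allocation in four would put a given active arm 20 points or more away from placebo, moving the ratio by about 4-12% for a 60/40 split. That is small beside the sampling error of arms that size. With 50 per arm, or with 10% untreated and 20 per arm, the chance is about 6% or less. Arm size, untreated share, rate ratio and allocation method are all assumptions. The case for stratifying is that it is cheap and must be decided early, not that the planned analysis is invalid.

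**What to change.** 1. Reconcile the design summary, the Inclusion Criteria and Sample Size Estimation, so that the adjuvant statement, and the ethical ground built on it, describe the patients who are eligible.
2. State that the target is the pooled effect in relapsing-remitting patients with or without background interferon beta or glatiramer acetate.
3. Stratify the central HIONU scheme by background treatment at enrolment: interferon beta or glatiramer versus none.
4. Include that two-level factor in the relapse-rate and Cox models as one of the pre-specified covariates already provided for, and give estimates by stratum descriptively.

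The cost is a few incomplete blocks and one degree of freedom. The factor is already recorded for each patient, so no new data are needed. How untreated patients should be managed is a clinical matter and is not addressed here.

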At The Cyprus Institute of Neurology And Genetics By PALUPA Medical Ltd. (Incubation Company)

Any and all information presented in this document shall be treated as confidential and shall remain the exclusive property of PALUPA Medical Ltd. The use of such confidential information must be restricted to the recipient for the agreed purpose and must not be disclosed, published or otherwise communicated to any unauthorized persons, for any reason, in any form whatsoever without the prior written consent of PALUPA Medical Ltd.

Project Title:

Proof-of-Concept Clinical Trial:

Novel medical nutrition formulas as possible new approach for relapsing multiple sclerosis treatment: a double-blind, randomized, placebo-controlled proof-of-concept clinical trial.

Clinical Trial Protocol and Project Design

Completed

Version Number: electronic version FINAL

Date: 1st June 2005 Total number of pages: 16

PALUPA Medical Ltd.

Project Funded By: Cyprus Ministry of Commerce, Industry and Tourism, program for the creation of new high technology and innovation enterprises through the business incubator.

PROTOCOL

Medical Nutrition Formulas for the Treatment of Relapsing Multiple Sclerosis

A Single-Center, Parallel-group, Proof-of-Concept, Double-blind, Randomized, Placebo-Controlled, Trial of Efficacy and Safety.

Purpose

The purpose of this proof-of-concept study is to determine the safety and efficacy of three novel

interventions in the treatment of individuals who have been diagnosed with relapsing remitting

multiple sclerosis (MS). We intend to evaluate the therapeutic ability of PLP10 and of two other

interventions consisting of PLP10 constituent partial fractions versus placebo, when used in

patients with relapsing remitting (RR) MS. It is hoped that the agents used for the composition of

the interventions in general will be able to normalize structural molecules of cell membranes,

normalize phospholipase function and immune system, normalize endoplasmic reticulum

function/stress, specific gene expression, quench free nitro- and oxo- free radical derivatives,

elevate anti-inflammatory cytokines, halt apoptosis, normalize metalloproteinases function,

supply major building blocks for myelin formation/reformation, promote remyelination and

neuroprotection and so halt inflammation and all related cascade of events leading to the MS

pathogenesis. All these simultaneously involved pathogenic mechanisms as a result of multiple

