Due to the nature of the intervention ingredients/agents the protocol of the clinical study is considering a normalization period for the interventions' agents to exert their beneficial effect. The normalization period is used: (a) because the incorporation/normalization of the immune cells' membranes by dietary oral agents is a long time process, (b) because the T-lymphocytes are produced in a very slow rate in adulthood and even much slower in older people, (c) because oral fatty acids need 6 months to have a neurological effect in animal models, (d) to eliminate any placebo effect and regression to the mean, and finally (e) to correct specific body lipid deficiency, and thus accurately record the efficacy as a result of the interventions. It is strongly suggested that specific lipid deficiency need to be "corrected and things be normalized as much as possible" before evaluating their effect.

Primary end points

Primary outcome will be the annual relapse rate (ARR)

- The study is designed to end 30 months after enrolment and neurological and clinical assessments should be scheduled at entry baseline (6 months after enrollment, the end of normalization period) and at 3, 9, 15, 21 and 24 months on-treatment. A 12 month (extension) period (free of intervention) will be followed with relapse recording.
- Patients should be examined within 48 hours after the onset of new neurological symptoms for the treating physician to confirm and record the relapse as per protocol.

Relapses are defined as new neurologic symptoms or worsening of pre-existing symptoms (that are stable for at least 1 month) not associated with fever or infection that lasts for at least 24 hours and characterized by new or worsening neurological signs on examination.

The Key Secondary end point will be the time to confirmed disability progression

Time to confirmed disability progression is defined as an increase of 1.0 on the EDSS from a baseline score, confirmed after 6 months, with an absence of an ongoing relapse at the time of assessment (progression cannot be confirmed during a relapse) and with no documented relapse during the 6-months period needed for the confirmation. Under the same conditions as previously discussed, the final EDSS score should also be confirmed 6 months after the end of the study.

A post-hoc analysis

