Baseline characteristics will be compared across all intervention groups by ANOVA or Kruskal-Wallis rank test for continuous variables and by an exact chi-squared test for categorical variables, as appropriate.

Each test will be performed with a significance level of 0.05 (P-values will be two-tailed).

Primary Endpoint

Annualized Relapse Rate (ARR):

A Poisson regression/ negative Binomial analysis will be used to analyze this endpoint. The analysis will allow for likely overdispersion due to within-subject correlations by basing standard errors on the empirical estimator of the parameter covariance matrix. The fixed factors in the model will include treatment and relevant pre-specified covariates.

The relapse rate will be calculated as the total number of relapses divided by the total number of patient-years followed for each treatment group. ARR differences will also be calculated among all comparable parameters and reported as percent difference (relative reduction).

Secondary Endpoint

Time to Confirmed Disability Progression:

For the secondary end-point outcome, the time to disability progression, Kaplan–Meier curves will be constructed. A Long-rank and Cox proportional-hazards regression model will be used to analyze this endpoint. The fixed factors in the model will include treatment and relevant prespecified covariates . Additional baseline characteristics will be considered for inclusion in secondary models.

If the usual normality assumptions are not met, the endpoints will then be analyzed by either Poisson regression, using a model similar to the one to be used for the ARR, Wilcoxon Rank-Sum tests, or proportional odds logistic regression models, depending on the nature of the endpoints and whether covariates will be included in the model.

Safety

All treatment emergent signs and symptoms (those that initially occur after taking the first dose of study medication, or those that worsen after taking the first dose of study medication) will be summarized and tabulated according to their severity (mild, moderate, or severe) and relationship (definitely not related, or related) to study medication. The rates will be compared between each group and placebo using Fisher's Exact test.

Missing Data

Missing data of the lost to follow patients will be imputed by use of the last-observation-carried-forward (LOCF) approach.

We thank every and each one of you, for your total cooperation.

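### The either-endpoint success rule does not hold false success at the 5% used for each test, leaves the deciding comparison open, and lets the key secondary endpoint alone declare success

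*Protocol*

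**What the plan says.** - **Success rule** (Brief Statistical Methods): "The study will be considered successful if there is a significant difference between the treatments for either of the two endpoints".
- **Level** (same section): "Each test will be performed with a significance level of 0.05 (P-values will be two-tailed". No split, order or adjustment follows.
- **Arms** (Randomization and Masking): "Patients will be randomly assigned to the four intervention groups". These are A, B (PLP10), C and placebo. No allocation ratio is given.
- **Ranking of endpoints** (Primary end points): ARR is named as the primary outcome, and then "The Key Secondary end point will be the time to confirmed disability progression". Missing Data Handling repeats the order, with relapses first and disability second.
- **Intended comparison** (Purpose): "We intend to evaluate the therapeutic ability of PLP10 and of two other", continuing "interventions consisting of PLP10 constituent partial fractions versus placebo, when used in" relapsing-remitting patients.
- **ARR analysis** (Primary Endpoint, under Brief Statistical Methods): "A Poisson regression/ negative Binomial analysis will be used to analyze this endpoint", with treatment as a fixed factor. The text adds: "ARR differences will also be calculated among all comparable parameters and reported as percent difference (relative reduction". The Cox model for progression also carries treatment as a fixed factor.

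**The concern.** The rule has three weaknesses.

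1. **Error rate.** Success needs only one significant result from several tests, each run at the full 0.05. The chance of at least one false positive is therefore above the level of any single test.
2. **Undefined comparison.** The rule names neither PLP10 nor placebo. Read literally with two-tailed tests, a difference between A and C satisfies it, and so does one in favour of placebo. Neither matches the stated purpose.
3. **Ranking without effect.** ARR is primary and progression is key secondary, yet a significant result on progression alone, with ARR failing, counts as full success.

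Sample Size Estimation says that no power calculation was possible. This sentence is therefore the only pre-stated standard by which the trial will be called positive or not. If the comparison can be settled after the data are seen, a declared success is hard to weigh.

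**Working it through.** **Inputs from the protocol:** 4 arms; 2 endpoints joined by OR; two-sided 0.05 per test (critical value 1.96). The protocol states no study-wise error figure, so there is none to reproduce. A single test at its stated level has 5% error.

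**Assumptions, not in the protocol:** equal allocation; no true difference on either endpoint; approximately normal test statistics that each hold 5%; correlation ρ between the endpoints, varied from 0 to 1.

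**Step 1: count the tests under each reading.**
- One 3-df test of the treatment factor per endpoint: 1 × 2 = 2.
- Each active arm against placebo: 3 × 2 = 6.
- Every pair of arms: 6 × 2 = 12.

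**Step 2: reference value if all tests were independent**, 1 − (1 − 0.05)^k.
- k = 2: 1 − 0.95² = 9.75%.
- k = 6: 1 − 0.95⁶ = 26.5%.
- k = 12: 1 − 0.95¹² = 46.0%.

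Pairwise tests share arms and are therefore correlated, so the last two figures are too high.

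**Step 3: simulation with the shared arms built in** (1,000,000 draws for each ρ). Arm results on endpoint 1 are X₁…X₄, independent N(0,1). On endpoint 2 they are ρX + √(1 − ρ²)·e, with e independent N(0,1). The pairwise statistic is Z = (Xᵢ − Xⱼ)/√2, significant if |Z| > 1.96. The global statistic is Σ(Xᵢ − X̄)², significant above the 95th percentile of chi-square with 3 df. Success is any significant result on either endpoint.

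| Reading of the rule | ρ = 0 | 0.5 | 0.7 | 0.9 | 1 |
|---|---|---|---|---|---|
| One global test per endpoint | 9.7% | 9.2% | 8.5% | 7.2% | 5.0% |
| PLP10 vs placebo only | 9.7% | 9.1% | 8.3% | 7.0% | 5.0% |
| Three active arms vs placebo | 23.4% | 22.0% | 20.2% | 17.3% | 12.5% |
| Same, only results favouring active | 12.1% | 11.1% | 10.1% | 8.7% | 6.3% |
| All six pairs | 36.5% | 34.1% | 31.4% | 27.1% | 20.3% |

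The fourth row should be set against 2.5%, the chance that one two-sided 0.05 test falsely favours the active arm.

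**Step 4: can the error be controlled with all three arms kept?** Yes. Bonferroni at 0.05/6 = 0.0083 over the six tests against placebo gives 4.6% (ρ = 0) or 4.3% (ρ = 0.5). For all pairs, 0.05/12 = 0.0042 gives 4.3% or 4.2%.

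**The case against.** **The global-test reading.** A reader might infer that at least six tests feed the rule and that false success is therefore 20% or more. The protocol does not support that as a flat statement. It asks for a difference among treatments and enters treatment as a fixed factor in both models, so one global test per endpoint is an equally literal reading, with about 8–10%. Pairwise testing against placebo is well supported by the Purpose section, by the post-hoc MRI comparison of the most effective intervention with placebo, and by the safety comparison of each group with placebo. It is not specified for efficacy, however. The all-pairs reading has the weakest support, because the sentence on ARR differences describes reporting percentages rather than tests that decide success. This objection stands, and it is why the size is given by reading.

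**No promise of 5% overall.** A reader might infer that the protocol breaks a stated study-wise guarantee. It does not: 0.05 is stated for each test only.

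**PLP10 remains interpretable.** A reader might infer that a positive result would say nothing about PLP10. That goes too far. Restricted to PLP10 against placebo on two endpoints, the error is about 8–10%, roughly double the per-test level, and such a result can be read with that caveat.

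**Proof of concept, and a possible SAP.** The trial is Phase II and seeks an indication of efficacy, and details of contrasts and multiplicity are often left to an SAP. This lowers the consequence but does not remove the defect. The protocol itself fixes the either-endpoint rule and the full 0.05 per test, so an SAP that controlled the error would have to override it.

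**Conclusion.** The point holds, with a size that depends on the reading. For ρ from 0 to 0.7 and equal arms, false success is about 8–10% with one global test per endpoint, 20–23% with each active arm against placebo (10–12% counting only results favouring active), and 31–36% with all pairs. Higher correlation lowers these figures. The rate falls to 5% only if a single test per endpoint counts and the endpoints are perfectly correlated. The documents do not settle which reading applies, and that openness is part of the defect. The conflict between the success rule and the ranking of ARR over progression needs no assumption, since it follows from the text alone.

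**What to change.** Replace the success sentence with one that fixes the following:

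- **Success** is superiority over placebo on ARR, in the analysis population that the protocol designates as key.
- **Error across the active arms** is held at two-sided 0.05 overall, either by a fixed sequence starting with PLP10 against placebo or by Holm or Bonferroni over the three comparisons with placebo. Putting PLP10 first is one acceptable choice. The protocol sets out to evaluate all three interventions, so keeping them on an equal footing is also defensible.
- **Progression** is tested only for an arm that has won on ARR, by a stated procedure that keeps the overall error at 0.05. In a fixed sequence, it takes a named place after that arm's ARR test. With Bonferroni, each arm has 0.05/3 = 0.0167 and progression is tested at that same level after a win on ARR, so the total is at most 3 × 0.0167 = 0.05. With Holm, an arm's share passes to the other arms' ARR tests and cannot also be spent on its progression test, so the text must say which is intended.
- **All other comparisons** are reported as estimates with confidence intervals and without a success claim.

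The change is to wording only. The price is a lower chance of a formal claim for arms tested later or at a stricter level, and no formal claim on progression when ARR fails. Whether the per-protocol or the intention-to-treat population should decide (Missing Data Handling makes per-protocol the key analysis) is a separate question that this fix leaves untouched.
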